**Variables:**

- COVID-19 vaccinations will be identified from a vaccination registry linked with each patient's primary care clinical history.
- Medically attended diagnosis of COVID-19 in any setting will be identified through linked registries of 1) COVID positive test results, 2) hospital COVID diagnosis or discharged COVID diagnosis.
- Covariates will be collected from primary care eHR. Covariates will include demographic information, morbidities, medication use, health care utilisation, markers of current disease status at time zero, and markers of frailty.

**Data sources:** Base de datos para la Investigacion farmacoepidemiológica en Atención Primaria (BIFAP) and linked registries of 1) COVID positive test results, 2) hospital COVID diagnosis or 3) discharged COVID diagnosis

**Study size:** BIFAP database includes up-to-standard information for around 7.7 million patients aged  $\geq 18$  years.

**Data analysis:** Characteristics of the vaccinated and unvaccinated groups at baseline will be described. Incidence rates of COVID-19 outcomes will be calculated and compared between the two groups, and vaccine effectiveness measures will be estimated by 1 minus the hazard ratios (HR; 95%CI). Additional time period-specific effect estimates (e.g., at 3, 6, or >6 months after vaccination) will also be estimated.

Stratified analysis will separately estimate vaccine effectiveness in clinically meaningful subgroups and calendar periods. Sensitivity analyses will evaluate the robustness of the study approach across variations of the study methodology.

**Milestones:** Evaluation of the availability of data will start during 1-15 June but timelines may be impacted by the date the data are received from the different regions and BIFAP common data model is ready for evaluation (End of July).

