#### **9.1.1.5 Assess Potential for Unmeasured Confounding**

Unmeasured confounding is a serious threat to the estimation of vaccine effectiveness using observational data [3-9]. There may be situations where the initial recommendations for vaccination, the vaccine distribution strategy, and the uptake of the vaccine may heavily influence the magnitude and direction of confounding. Since unmeasured and unknown confusion may be present we will perform the following strategies in order to minimise then:

- unvaccinated comparator will be matched by time zero of the vaccinated pair, birth year cohort (year; it will be broad till 2-years if not enough patients to select), sex, region of the primary care practice. If available information, patients living at nursing home will be matched). Several other confounder will be controlled for through adjustment in the Cox model.
- Since multiple COVID-19 vaccines are available, recipients of different COVID-19 vaccines will be also compared with the same unvaccinated comparator and among them in a head-to-head fashion. This choice would greatly diminish, if not eliminate, confounding by indication.

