### 9.3.1 Exposure Assessment and Time At Risk

Data will be collected from BIFAP database with data from Spain (described in [Data Sources](#)).

**Inclusion criteria** to the Source population: up-to-standard,  $\geq 1$  year baseline information in January 2021 in BIFAP. The last date of filling all the inclusion criteria will be the inclusion date. No restriction to age or sex will be applied.

**Exclusion criteria:** Patients with prevalent COVID vaccinations or infections ever before (i.e. washout period) the inclusion criteria will be excluded.

**Stop date:** the last moment of the following criteria will define the stop date to contribution: covid-19 infection, death, loss to follow-up and end of study period (the last date available in the data source at data collection).

**Exposure assessment:** The 1st vaccination recorded after the inclusion date will be the time zero for patients included in the vaccinated group, as explained in section 'Definition of Time Zero' [9.1.1.4](#).

From the source population, 10 individuals unvaccinated on or before time zero of the vaccinated pair (10:1) will be randomly selected among those with similar birth cohort, sex and region (matched criteria). Patients included in the comparison group, may be vaccinated later during their follow-up period and then contribute to the vaccinated group (from the date of vaccine administration ahead; i.e. time zero for the vaccinated group).

\*Note: All individuals vaccinated during their follow-up contribution will be included in the vaccinated group. While, a random selection of the unvaccinated individuals will be included as unvaccinated group.

The date and type of vaccine administered will be collected from the **Table of Vaccine** from BIFAP data model. In particular, Covid-19 vaccinations will be ascertained from official covid-19 vaccination registries and provided by the regional governments. The coding system is not known yet. The feasibility analysis will include an evaluation of the coding type, whether or not vaccines are recorded according to standardised system or not. We expect that either ATC07 (J07????) or National Code (CNF [Código Nacional de

Farmacia]) specific for pharmaceuticals in Spain is available for all vaccines administered.

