### **9.3.2 Eligibility Criteria**

No additional eligibility criteria are needed to define the cohort.

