Health care utilisation in the year before time zero and updated will be evaluated as measures of health care-seeking behaviour, overall health status, and access to health care. Additionally, short-term health care utilisation in the 2 weeks before and including time zero and updated will be recorded separately, as short-term markers of current health status may influence individuals' vaccination decisions. Considered variables will include the following:

- Primary care utilisation (number of visits to PC)
- Influenza vaccination (number in the previous 5 years)
- Other vaccinations (number in the previous 5 years)
- COVID-19 tests (total number)

Frailty has been demonstrated as a confounder of vaccine-outcome associations in older adults [5,6,9]. Additional personal characteristics demonstrated to be associated with frailty [6,31,32] should be included as confounding factors, and may include the following:

[figure not shown]
- Wheelchair use
- Home hospital bed
- Paralysis
- Parkinson's disease
- Skin ulcer

- Weakness
- Stroke/brain injury
- Ambulance transport
- Dementia
- Difficulty walking
- Home oxygen
- Rehabilitation care
- Psychiatric illness
- Sepsis
- Heart failure
- Podiatric care
- Bladder continence
- Diabetes complications
- Arthritis
- Coagulation deficiencies
- Vertigo
- Lipid abnormalities

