## 9.4 Data Source

Data on patients will be obtained from primary care outpatient anonymised clinical records, dispensation in pharmacies of primary care prescriptions and diagnosis at hospital discharge from the Spanish public National Health System (SNS). Those data banks are unified in the data source so-called "Base de datos para la investigación Farmacoepidemiológica en Atención Primaria" (BIFAP) (8,9).

BIFAP includes information about patients' age, sex, life-style factors (i.e. body mass index (BMI), smoking status, alcohol consumption), clinical events (recorded by using

the International Classification of Primary Care (ICPC) and the International Classification of Diseases 9th Revision (ICD-9) medical terms (6,7)), anonymised primary care physicians' (PCPs) free-text notes, specialist referrals and discharge letters, prescriptions issued in primary care and their dispensations in pharmacies, vaccinations, laboratory test results and diagnosis at hospital discharge (recorded through the RAE-CMBD system) of around 13.7 million patients attended in a public primary care setting (7.4 of them aged  $\geq 18$  years). BIFAP covers 7 out of 19 districts in Spain and 57% of their population overall (as described in the Spanish Statistical Office (10)). In addition, currently, data on covid-19 infections resulting in an admission or discharge diagnosis to hospital (inpatient record) or intensive care unit as the setting of care are being incorporating to BIFAP. Figure 2:

BIFAP is fully funded by the Spanish Agency on Medicines and Medical Devices (AEMPS), belonging to the public Department of Health, and is maintained with the collaboration of the participant regions (8).

The records on the results of the COVID-19 laboratory test will be linked with BIFAP primary care profiles. Also, all vaccinations administrated against COVID-19 recorded in any setting will be linked with the primary care history in regions providing data. Particularly, vaccinations will be entered in the BIFAP's Table of Vaccines that in 2019 included around 61 million of recorded vaccinations.

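### People in hospital at time zero can be drawn as unvaccinated comparators, and the 2-week current-health window names no hospital contact that would identify them; some upward bias in early-window VE and VE against COVID-related death is likely.

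*Protocol*

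**What the plan says.** **Who may be a comparator.** Section 9.3.1 samples as follows: "10 individuals unvaccinated on or before time zero of the vaccinated pair (10:1) will be randomly selected among those with similar birth cohort", with sex and region as the other criteria. Section 9.1.1.5 describes the same matching ("unvaccinated comparator will be matched by time zero of the vaccinated pair, birth year cohort", sex and region) and adds nursing-home residence if that information exists. The only exclusion is in 9.3.1: "Patients with prevalent COVID vaccinations or infections ever before (i.e. washout period) the inclusion criteria will be excluded". Section 9.3.2 closes the list: "No additional eligibility criteria are needed to define the cohort".

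**What is measured about current health.** Section 9.3.4 records health care utilisation over the previous year and, separately, over the 2 weeks up to and including time zero. The reason given for the short window is that current health may affect the decision to be vaccinated. The listed variables are "Primary care utilisation (number of visits to PC"), influenza and other vaccinations, and "COVID-19 tests (total number"). Comorbidities, comedications and a list of candidate frailty markers are described separately.

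**What the data source holds.** Section 9.4 includes "laboratory test results and diagnosis at hospital discharge (recorded through the RAE-CMBD system") among the contents of BIFAP. The Abstract says "Covariates will be collected from primary care eHR".

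**The concern.** The protocol makes an exchangeable comparator the centre of its design (9.1), and in 9.1.1.4 it aligns eligibility, covariates and follow-up at time zero. Inpatient status on that day breaks the symmetry. Attending for a campaign dose largely selects people who are not acutely ill in hospital. A random draw from everyone unvaccinated with the same birth cohort, sex and region does not.

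People in hospital or just discharged plausibly have a higher rate of detected infection and of death after infection. If they sit mostly on the unvaccinated side, the comparator rate rises and VE looks better than it is.

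The variable intended to catch this does not see it. Someone who spent those 2 weeks in hospital would tend to have few or no primary-care visits, so the short window may class a very ill comparator with healthy people who had no reason to attend.

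The early windows matter because 9.1.1.4 divides follow-up after the first dose in order to see when the effect begins. Spurious early protection could be read as early onset of effect.

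**Working it through.** **1. The plan's own figure.** Table 1 gives a probability of 1 that the upper 95% limit of the risk ratio lies below 1. It reproduces. For Janssen at 1:1:

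- 7,720,843 / 2 = 3,860,421.5 per group
- expected unexposed cases: 3,860,421.5 × 0.0006057 = 2,338
- expected exposed cases: 2,338 × 0.331 = 774
- SE of ln RR ≈ √(1/774 + 1/2,338) = 0.0415
- −ln(0.331)/0.0415 − 1.96 = 26.6 − 1.96 ≈ 24.7, so the probability is 1

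This covers random error only. It says nothing for or against the present point.

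**2. Can an inpatient be a comparator?**

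| Place | Rule | Removes an inpatient? |
|---|---|---|
| 9.3.1 sampling | unvaccinated; similar birth cohort, sex, region | No |
| 9.3.1 exclusions | earlier COVID vaccination or infection | Only those already recorded with COVID |
| 9.3.2 | nothing further | No |
| 9.1.1.5 matching | nursing home, if available | No |

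**3. Can the covariates identify one?** The 2-week items are primary-care visits, vaccination counts and tests. None is a hospital contact. Ambulance transport, rehabilitation care, home oxygen and sepsis appear among the frailty markers, but that list is optional, and the backward selection in 9.7.3.2 can drop any item by p-value.

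**4. How large could the bias be?** Let f be the excess share of inpatients among comparators at time zero, and R their outcome rate relative to other comparators. Without adjustment,

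observed HR = true HR / (1 − f + fR).

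The documents give neither f nor R. Assumed ranges: f from 0.1% to 1%, R from 5 to 30.

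| f | R | 1 − f + fR | true VE 0% | true VE 66.9% | true VE 70.4% | true VE 95% |
|---|---|---|---|---|---|---|
| 0.1% | 5 | 1.004 | 0.4% | 67.0% | 70.5% | 95.0% |
| 0.5% | 10 | 1.045 | 4.3% | 68.3% | 71.7% | 95.2% |
| 1% | 5 | 1.040 | 3.8% | 68.2% | 71.5% | 95.2% |
| 1% | 30 | 1.290 | 22.5% | 74.3% | 77.1% | 96.1% |

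Worked case, last row: 1 − 0.01 + 0.01 × 30 = 1.29; 1 − 0.331/1.29 = 74.3%. The values 66.9%, 70.4% and 95% are the Table 1 effectiveness assumptions.

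A second set of assumptions (share 0.2% to 1.5%, rate ratio 5 to 20) gives factors from 1 + 0.002 × 4 = 1.008 to 1 + 0.015 × 19 = 1.285. A true VE of 0% would then appear as 0.8% to 22.2%.

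**5. When would it act?** The imbalance is greatest just after time zero. The main analysis in 9.1.1.4 starts 15 days after the full series. With the 21- or 28-day dose interval in 9.3.1, that is 21 + 15 = 36 or 28 + 15 = 43 days after time zero, by when most people in hospital on day 0 would probably have left hospital or died. For a one-dose vaccine the main window opens 15 days after time zero, so less of the effect will have faded.

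**The case against.** A reader might infer that primary-care visits are the only contact covariate, that very ill comparators always look like low users of care, and that VE against hospitalisation and death is therefore inflated throughout. The documents do not support that.

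- **Covariates.** Tests and vaccinations are also counted, and several frailty markers reflect intensive care needs. Comorbidities are taken ever before time zero, and comedication also comes from pharmacy dispensing. Section 9.3.4 leaves room for further risk factors. Adjustment is therefore partial, not absent.
- **Low users.** This fits the 2-week window. Over one year, very ill people may well have many primary-care visits.
- **Hospitalisation.** Section 9.3.3.3 dates the event at admission. For someone already in hospital at time zero, that date precedes follow-up, so an infection acquired during the stay is not clearly a countable event. The protocol does not say how to treat it.
- **Death.** Section 9.3.3.5 counts deaths within 8 weeks of a COVID date, and the COVID-specific definition in 9.3.3.4 also requires a COVID link. General inpatient mortality without COVID does not enter, so nothing in the documents supports a very large R.
- **Direction.** Section 9.9 describes the opposite possibility, that sicker people are vaccinated earlier, which would lower VE. It also allows for upward bias from more careful people being vaccinated. Neither passage mentions inpatients.

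These points limit the size and reach of the concern. They do not close the eligibility gap or supply a 2-week variable that identifies an admission.

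**Conclusion.** The gap is fixed by the eligibility text and is not detail left to an analysis plan: a current inpatient is an eligible comparator, and the window designed for current health cannot recognise one. The likely direction is upward for VE, provided that inpatients are over-represented among comparators and have a higher outcome rate. Both conditions are plausible, but neither is documented.

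The effect should be concentrated in the D1 induction and D1 effectiveness windows and in COVID-related death, and be smaller in the main analysis. It is small when true VE is near 95%. It could matter where true VE is low, as it may be in the early windows. The figures above are unadjusted illustrations on assumed inputs, not estimates of the actual bias, and the upper ends need both a 1% excess share and a rate ratio of 30. The point merits a protocol change because the remedy is specific and cheap, not because a large bias has been shown.

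**What to change.** - **Section 9.3.1.** Where linked hospital records give admission and discharge dates, require that neither the vaccinee nor the comparator is an inpatient on time zero (admission date ≤ time zero ≤ discharge date). The rule must be the same for both. It also removes the undefined case of a hospitalisation dated before follow-up.
- **Section 9.3.4.** Add two baseline covariates: the number of admissions in the previous year, and any inpatient day or discharge in the previous 2 weeks. Exempt both from the stepwise selection in 9.7.3.2 so that they stay in the model.
- **Section 9.1.1.1.** Add to the feasibility check whether all-cause stay dates are available, and in which regions. Section 9.4 documents discharge diagnoses and says that COVID admissions are still being added, so the dates cannot be taken for granted.

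Cost: protocol wording, one further extraction, and a small loss from a 10:1 comparator pool. The rule can apply only in regions with linked stay dates; section 9.3.3.3 already accepts a regional restriction for the hospitalisation outcome.

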**Population:** Individual aged  $\geq 18$  years with at least 1 year of record with their primary care physician from December 2020 till April 2021.

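### Prior vaccinations are counted over 5 years, but entry needs only 1 year of record and nothing accounts for record length, so the counts are truncated for people with short records

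*Protocol*

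**What the plan says.** Among the health care utilisation covariates, Protocol section 9.3.4 lists "Influenza vaccination (number in the previous 5 years") and "Other vaccinations (number in the previous 5 years"). The sentence that opens the list sets a shorter general window: "Health care utilisation in the year before time zero and updated will be evaluated as measures of health care-seeking behaviour".

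For entry, section 9.3.1 asks for at least 1 "year baseline information in January 2021 in BIFAP", and the abstract (section 4) likewise describes individuals "with at least 1 year of record with their primary care physician". Section 9.3.2 adds nothing: "No additional eligibility criteria are needed to define the cohort". Comparators are "randomly selected among those with similar birth cohort, sex and region (matched criteria"); section 9.1.1.5 adds time zero and, if the information is available, nursing-home residence. Record length is not a matching factor, and it is not among the covariates of section 9.3.4.

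Section 9.7.5 gives people with missing confounder values a missing category and plans no imputation for them.

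**The concern.** The two vaccination counts are the listed covariates closest to a person's past willingness to be vaccinated. The protocol treats that behaviour as a serious source of confounding: section 7 names adherence to vaccination recommendations, and section 9.9 says that effectiveness would be biased upward if more adherent people were vaccinated more.

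A raw count over a window that is only partly observed mixes behaviour with length of record. Someone vaccinated every season but with a short record can carry the same value as someone with a full record who was vaccinated once. The missing category would not separate them, because a vaccination given before the record began shows as a lower count or as 0, not as missing. What is at stake is incomplete control of prior vaccination behaviour in people with short records, and some residual confounding in the adjusted VE.

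**Working it through.** The protocol gives no figure of its own to reproduce here. The check compares the two windows and then tests how much the mismatch could matter.

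**Inputs from the protocol**
- Count window: 5 years (9.3.4).
- Minimum record: 1 year in January 2021 (9.3.1; abstract).
- Influenza vaccination campaign: September to December (9.1).
- Matching: 10 unvaccinated to 1 vaccinated (9.3.1).

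**Inputs not in the protocol, so assumed**
- Share of people with under 5 years of record: 5% to 30%.
- Annual influenza vaccine uptake *u*, with years independent.
- For the VE illustration: influenza-vaccine seekers are 60% of the vaccinated and 40% of the unvaccinated; hazard ratio (HR) for infection in seekers 0.7; true vaccine HR 0.3 (VE 70%).
- Earlier vaccinations are not back-filled.

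**Step 1. Observable share of the window.** For a record of *L* years (up to 5) this is *L*/5:

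| Record (years) | Observable share |
|---|---|
| 1 | 20% |
| 2 | 40% |
| 3 | 60% |
| 4 | 80% |
| 5 | 100% |

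A record that starts in January 2020 holds one autumn campaign (2020) by January 2021, so an every-season vaccinee shows 1 of 5. The share is slightly above 20% if time zero falls later in 2021.

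**Step 2. Effect on the count.** The expected count is *u* × *L*, and the chance of a count of 0 is (1 − *u*)^*L*. At *u* = 0.5:
- 1 year of record: expected count 0.5, chance of 0 = 0.5 = 50%.
- 5 years of record: expected count 2.5, chance of 0 = 0.5^5 = 3.1%.

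**Step 3. Effect on the cohort mean count.** With share *s* of the cohort having *L* years of record, the mean falls by *s* × (1 − *L*/5):
- All short records 1 year: 0.05 × 0.8 = 4% to 0.30 × 0.8 = 24%.
- Short records averaging 3 years: 0.05 × 0.4 = 2% to 0.30 × 0.4 = 12%.

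**Step 4. Effect on VE.** Treat the covariate as seeker yes/no, and let a share *s* of seekers be recorded as non-seekers. Per unit of vaccinated person-time and 10 units of unvaccinated person-time, with *s* = 30%:
- Recorded seekers, vaccinated: time 0.6 × 0.7 = 0.42; events 0.42 × 0.7 × 0.3 = 0.0882.
- Recorded seekers, unvaccinated: time 10 × 0.4 × 0.7 = 2.8; events 2.8 × 0.7 = 1.96.
- Recorded non-seekers, vaccinated: time 0.18 + 0.40 = 0.58; events (0.18 × 0.7 + 0.40) × 0.3 = 0.1578.
- Recorded non-seekers, unvaccinated: time 1.2 + 6.0 = 7.2; events 1.2 × 0.7 + 6.0 = 6.84.
- Mantel-Haenszel rate ratio: (0.0882 × 2.8/3.22 + 0.1578 × 7.2/7.78) / (1.96 × 0.42/3.22 + 6.84 × 0.58/7.78) = 0.2227/0.7656 = 0.291, so VE is 70.9%.

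At *s* = 5% the same calculation gives 70.2%. If the covariate were lost for everyone, the ratio would be 0.3 × (0.6 × 0.7 + 0.4)/(0.4 × 0.7 + 0.6) = 0.3 × 0.82/0.88 = 0.280, so VE would be 72.0%. That is the ceiling under these inputs. Real truncation loses less than Step 4 assumes, because records of 2 to 4 years keep part of the history.

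**The case against.** The strongest reply is that the functional form of a covariate belongs in a statistical analysis plan, which was not available, and that section 9.3.4 leaves its list open. This stands in part. A scaling rule could be set elsewhere, but the protocol itself fixes the 5-year count and the 1-year entry rule, and nothing in it reconciles them.

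A second reply is that other parts of the plan address the same bias. Section 9.7.4.1 plans a subgroup of people vaccinated against influenza in the 2020-2021 season, aimed at adherence and preventive behaviour. That needs less than 1 year of record and is largely unaffected. Primary care visits and comedications use windows of a year or less and are also unaffected. This stands and keeps the point small.

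Third, using whatever history exists, up to 5 years, is a defensible way to keep information on people with long records, and comorbidities assessed at any time before time zero depend on record length in the same way. This is a reason to keep the counts, not to leave record length out.

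Three stronger readings are tempting, and the documents do not support them:
- A reader might infer that section 9.3.4 contradicts itself, with a 1-year lead sentence over 5-year items. The bracketed windows are specific and override the general sentence, so the list can be implemented as written.
- A reader might infer that influenza vaccination is undercounted by 80% in people with short records generally. That figure describes only an every-season vaccinee at the minimum record length, and only without back-filling.
- A reader might infer a material bias in VE. The protocol gives neither the distribution of record length nor influenza uptake, and the illustration does not show a material shift.

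**Conclusion.** The mismatch is real but minor. The plan counts prior vaccinations over 5 years in people who may have 1 year of record, and nothing in it accounts for the difference. For those with under 5 years of record the counts are truncated, and adjustment for prior vaccination behaviour is incomplete.

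This depends on earlier vaccinations not being back-filled into the Table of Vaccines. The protocol is silent on that: the registry linkage it describes in sections 9.1.1.3 and 9.4 concerns COVID-19 vaccinations. The share of the cohort affected is not given.

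The effect on VE is probably about 1 percentage point or less. That rests on the assumed inputs above, including that people who seek influenza vaccine have a lower infection hazard. If they test more and so have more recorded infections, the shift would go the other way. The point does not threaten the main conclusion of the study.

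**What to change.** In section 9.3.4, keep the two 5-year counts and add years of available record before time zero, capped at 5, as a covariate. Alternatively, express the counts per observed year and include the same term. Because section 9.7.3.2 selects covariates by p-value, state that the record-length term stays in the model whenever either count does. A single term corrects the average shift, not each person's value, so also add a sensitivity analysis restricted to people with at least 5 years of record.

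If the data holders know that vaccinations before registration are back-filled, one sentence saying so would largely answer the point.

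The cost is one extra covariate and one extra run on data already held. Per-year values from a single season are noisy. The restricted analysis is smaller and leaves out people who recently joined the database. It would also leave out children under 5 if section 9.3.1 ("No restriction to age or sex will be applied") governs rather than the adult population given in the abstract.
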